9.4.3.2 Analysis of key secondary efficacy endpoints

The main analysis of the key secondary endpoints (changes from baseline to Week 52 for each of pre-bronchodilator FEV1, AQLQ(S)+12 total score, ACQ-6 score and weekly mean ASD score) will quantify the effect of the initially randomized treatment at Week 52, regardless of the treatments that subjects actually received, or whether the subjects received other controller therapy/rescue medications, including for subjects who discontinued study treatment prior to Week 52. This analysis will therefore include all available data after treatment discontinuation. Missing data from study discontinuation will be modelled based on what was observed during the study using direct likelihood approaches, which is a valid approach under the assumption that data are missing at random (MAR).

Change from baseline for the key secondary endpoints in the tezepelumab group will be compared to that seen in the placebo group using a mixed model for repeated measures (MMRM) model. This model will be used to perform the statistical tests specified in Section 9.1,

and to estimate the treatment effect at Week 52 and its 95% confidence interval for each endpoint. The response variable in the model will be change from baseline at each scheduled post-randomization visit up to and including Week 52, and irrespective of whether the subject remained on treatment and/or took other treatments. Treatment, visit, region, age (adolescents or adults) and treatment by visit interaction will be included as factors in this model. Baseline of the corresponding endpoint will also be included in the model as a continuous linear covariate. Unstructured covariance will be assumed to model the relationship between pairs of response variables taken at different visits on the same subject. If the MMRM model fails to converge with unstructured covariance, the SAP will pre-specify the approach for selecting a simpler covariance structure. The Kenward-Roger approximation to estimating the degrees of freedom will be used for tests of fixed effects derived from the MMRM model.

Descriptive summaries of the key secondary endpoints will also be presented. Adjusted means from the MMRM model above will be displayed graphically over time and used to evaluate time of onset of effect.

The consistency of treatment effects across continuous and categorical demographic/baseline variables will be investigated in a similar manner to the primary endpoint. In the case of categorical variables, appropriate terms will be added to the MMRM model, including a treatment by visit by subgroup interaction term, to enable the treatment effects within each subgroup category at Week 52 to be estimated. Any further subgroup analyses, and exact definition of all relevant categories where needed, will be pre-specified in the SAP.

Sensitivity analyses on the key secondary endpoints will be performed, and will be fully specified in the SAP. These may include, but not necessarily be limited to, the same items considered for the primary endpoint in Section 9.4.3.1.

As a supportive analysis to the analysis of change from baseline in ACQ-6, the main ACQ-6 analysis described above will be repeated for change from baseline in ACQ-5 and ACQ-7 score using a similar MMRM model. Similar descriptive and graphical summaries will also be produced.

As further supportive analyses to the analyses of change from baseline in ACQ-6 and AQLQ(S)+12, responders/non-responders (as defined in Sections 8.1.6.2 and 8.1.6.3) will be summarized descriptively and analyzed using a logistic regression model with factors which will include treatment, region and age (adolescents or adults). Baseline of the corresponding endpoint will also be included in the model as a continuous linear covariate. Further details of the logistic regression models and how missing responses at Week 52 will be handled will be specified in the SAP.

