3.2.3.3 AQLQ(S)+12 and ACQ-6 responders

Other variables based on AQLQ(S)+12 to be reported at each time point include:

1. AQLQ(S)+12 responder (Yes=1/No=0):
 - Responder: Change from baseline AQLQ(S)+12 total score ≥ 0.5
 - Non-responder: Change from baseline AQLQ(S)+12 total score < 0.5
2. AQLQ(S)+12 response (Improved/No Change/Deterioration):
 - Improvement: Change from baseline AQLQ(S)+12 total score ≥ 0.5
 - No change: $-0.5 < \text{Change from baseline AQLQ(S)+12 total score} < 0.5$
 - Deterioration: Change from baseline AQLQ(S)+12 total score ≤ -0.5 .

Other variables based on ACQ-6 to be reported at each time point include:

1. ACQ-6 responder (Yes=1/No=0):
 - Responder: Change from baseline ACQ-6 score ≤ -0.5
 - Non-responder: Change from baseline ACQ-6 score > -0.5
2. ACQ-6 response (Improved/No Change/Deterioration):
 - Improvement: Change from baseline ACQ-6 score ≤ -0.5
 - No change: $-0.5 < \text{Change from baseline ACQ-6 score} < 0.5$
 - Deterioration: Change from baseline ACQ-6 score ≥ 0.5
3. Subject's asthma control as measured by ACQ-6 score:
 - Well controlled : ACQ-6 score ≤ 0.75
 - Partly controlled : $0.75 < \text{ACQ-6 score} < 1.5$
 - Not well controlled: ACQ-6 score ≥ 1.5 .

In the above, no imputations will be performed for missing values.

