4.2.5 Key secondary endpoints

4.2.5.1 Main analysis

The main analysis of the key secondary endpoints (changes from baseline to Week 52 for each of pre-bronchodilator FEV₁, AQLQ(S)+12 total score, ACQ-6 score and weekly mean ASD score) will quantify the effect of the initially randomised treatment at Week 52, regardless of the treatments that subjects actually received, or whether the subjects received other controller therapy/rescue medications, including for subjects who discontinued study treatment prior to Week 52.

This analysis uses a treatment policy strategy and will therefore include all available data after treatment discontinuation until the end of the planned treatment period.

Subjects will be encouraged to continue to undergo applicable study related visits/procedures for the full 52-week period even after premature discontinuation of IP. Consequently, subjects lost to follow-up, subjects who die, subjects who withdraw their consent and subjects who choose Option 3 for their follow-up should be the only source of missing information for the key secondary analyses apart from subjects who choose Option 2 for their follow-up, who will have missing pre-BD FEV₁ following discontinuing of IP until their Week 52 visit.

Missing data will be modelled based on what was observed during the study using direct likelihood approaches, which is a valid approach under the assumption that data are missing at random (MAR).

Change from baseline for the key secondary endpoints in the tezepelumab group will be compared to that seen in the placebo group using a mixed model for repeated measures (MMRM) model. This model will be used to perform the statistical tests of the null hypotheses specified in [Section 4.1.1](#), and to estimate the treatment effect at Week 52 and its 95% confidence interval, for each endpoint.

The response variable in the model will be change from baseline at each scheduled post-randomisation visit up to and including Week 52, and irrespective of whether the subject remained on treatment and/or took other treatments. Treatment, visit, region, age (adolescents or adults) and treatment by visit interaction will be included as factors in this model. Baseline of the corresponding endpoint will also be included in the model as a continuous linear covariate. Baseline by visit interaction will not be included as a covariate in the MMRM model.

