4.2.5.4 Supporting analyses

As a supportive analysis to the analysis of change from baseline in ACQ-6, the main ACQ-6 analysis described in [Section 4.2.5.1](#) will be repeated for change from baseline in ACQ-5 and ACQ-7 score using a similar MMRM model. Similar descriptive and graphical summaries will also be produced.

The analysis of AQLQ(S)+12 total score change from baseline will be repeated for change from baseline in each of the 4 AQLQ(S)+12 domain scores using a similar MMRM model.

The analysis of ACQ-6 score change from baseline will be repeated for change from baseline in each of the 6 individual ACQ-6 items using a similar MMRM model.

As further supportive analyses to the analyses of change from baseline in ACQ-6, AQLQ(S)+12 and weekly mean ASD, responders/non-responders will be summarised descriptively and analysed using a generalised linear model for repeated measures, using a logit link function. The response variable in the model will be the binary responder status at each scheduled post-randomisation visit up to and including Week 52, irrespective of whether the subject remained on treatment and/or took other treatments. Treatment, visit, region, age (adolescents or adults) and treatment by visit interaction will be included as factors in this model. Baseline of the corresponding endpoint will also be included in the model as a continuous linear covariate.

In this model, inference will be based on generalised estimating equations (GEEs) using the method of [Liang and Zeger \(1986\)](#). An unstructured working correlation matrix will be used, along with empirically corrected standard errors. For the ASD responder endpoint, each of the 52 weeks used for weekly mean calculation will replace visit in the above model specification.

Only the first (responder/non-responder) ACQ-6 and AQLQ(S)+12 definitions in [Section 3.2.3.3](#) will be analysed using the repeated measures GEE analysis. The other categorical definitions in this section will be summarised descriptively only.

Change from baseline in the percentage of asthma symptomatic days (as defined in [Section 3.2.3.5](#)) will be summarised for the on-study period for each post-baseline week using descriptive statistics.

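### The responder GEE for ACQ-6, AQLQ(S)+12 and ASD is not generally valid under MAR and has no missing-data sensitivity analysis; the likely effect is modest and a MAR-compatible version is cheap to add

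*Protocol*

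**What the plan says.** - **Protocol 9.4.3.2.** As supportive analyses, ACQ-6 and AQLQ(S)+12 "responders/non-responders (as defined in Sections 8.1.6.2 and 8.1.6.3) will be summarized descriptively and analyzed using a logistic regression model", with treatment, region, age group and baseline score in the model. On missing data, it says that "how missing responses at Week 52 will be handled will be specified in the SAP". ASD responders are not mentioned.
- **SAP 3.2.3.3.** After the ACQ-6 and AQLQ(S)+12 responder definitions: "In the above, no imputations will be performed for missing values". SAP 3.2.3.7 repeats this for ASD responders.
- **SAP 4.2.5.4.** Responder status on all three scales is "analysed using a generalised linear model for repeated measures, using a logit link function", over all post-randomisation visits to Week 52 (52 weekly values for ASD). It adds that "inference will be based on generalised estimating equations (GEEs) using the method of" the standard reference for that technique, and "An unstructured working correlation matrix will be used, along with empirically corrected standard errors". The factors are treatment, visit, their interaction, region and age group, with baseline score as covariate. The section gives no weighting, no missing-data assumption and no fallback if the model does not converge.
- **SAP 4.2.5.1.** For the continuous scores: "Missing data will be modelled based on what was observed during the study using direct likelihood approaches", with MAR named as the assumption.
- **SAP 4.2.5.2.** MAR imputation, dropout-reason-based imputation (DRMI) and tipping-point analyses are planned for the four continuous key secondary endpoints only.
- **SAP Sections 1 and 6.** Section 1 says that departures from the protocol are described in Section 6. Section 6 does not list the move from logistic regression to GEE.

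The SAP is more explicit for other categorical endpoints. Section 3.2.4.1 counts non-completers as failures for the exacerbation-free endpoint, and 3.2.4.8 states the denominator for CGI-C and PGI-C. Neither a rule nor a denominator is given for responder percentages.

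**The concern.** A likelihood-based MMRM on the continuous score uses each subject's observed history and is valid under MAR if correctly specified. Unweighted GEE solves moment equations on the observed binary values and has no such general protection. If subjects leave because their recent score is poor, that information sits in the continuous score and is only partly carried by past responder status.

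The same scale could then give a mean difference and a responder odds ratio that disagree only because the two rest on different missing-data assumptions. Responder results are the clinical reading of three key secondary endpoints, and raw responder percentages are the figures most exposed. The missing-data sensitivity analyses would not reveal this, because they stop at the continuous scores.

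**Working it through.** **1. The plan's own figure.** No power is stated for responders. For the continuous scores, Protocol 9.2 gives 530 per arm, SD 1.3, difference 0.3 and nominal power of at least 95%; SAP 1.3 adds the two-sided 5% level.

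- Standard error = 1.3 × √(2/530) = 0.0799.
- Power = Φ(0.3/0.0799 − 1.96) = Φ(1.80) = 96.4%.
- Minimum detectable difference = 1.96 × 0.0799 = 0.157, against the stated 0.16.

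These figures reproduce, so SD 1.3 and difference 0.3 were carried into the simulations.

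**2. Simulation set-up.** From the documents: SD 1.3, difference 0.3, five post-baseline AQLQ(S)+12 visits, responder = improvement of 0.5 or more. Assumed: normal scores, between-visit correlations, placebo mean change, and a dropout model in which the chance of leaving rises as the last observed change gets worse. The 10% dropout in Protocol 9.2 is stated for the primary endpoint only. Region, age and baseline were not simulated.

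**3. Simulation A** (20,000 per arm). True Week 52 response is 56.0% v 65.1%, odds ratio 1.47. Each cell shows placebo v tezepelumab.

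| Dropout | Observed cases | GEE, unstructured | OR, independence GEE | OR, unstructured GEE |
|---|---|---|---|---|
| Unrelated to score, 10% v 10% | 56.1 v 65.1 | 56.1 v 65.1 | 1.46 | 1.46 |
| On last score, 10% v 10% | 58.6 v 67.5 | 56.9 v 65.8 | 1.47 | 1.46 |
| On last score, 20% v 20% | 61.2 v 70.0 | 57.9 v 66.7 | 1.48 | 1.45 |
| On last score, 15% v 5% | 59.8 v 66.3 | 57.3 v 65.5 | 1.32 | 1.41 |
| On last score, 5% v 15% | 57.3 v 68.8 | 56.5 v 66.3 | 1.65 | 1.52 |

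On the log scale, for 15% v 5%, the bias with independence is ln(1.323/1.468) = −0.104. With the planned unstructured matrix it is ln(1.411/1.468) = −0.040, so 1 − 0.040/0.104 = 62% is removed. For 5% v 15% the bias falls from +0.116 to +0.033, and 72% is removed.

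**4. Two checks in a further run** (12,000 per arm, true odds ratio 1.44).

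- If dropout depends only on past responder status, the unstructured GEE gives 1.44 with equal and with unequal dropout.
- Maximum likelihood on the continuous score gives 0.278 to 0.287 against a true 0.284, including the case where the GEE gives 1.38 (15% v 5% on last score).

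**5. Simulation B** (30,000 per arm, correlations 0.52 to 0.70). True response is 62.4% v 70.3%, odds ratio 1.43.

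- Placebo subjects leave for poor response (12%), tezepelumab subjects for unrelated reasons (9%): observed cases 65.8% v 70.4%, a difference of 4.6 points instead of 7.9. The GEE odds ratio is 1.37, and 1.35 with 16% v 8% dropout.
- Same mechanism in both arms: odds ratio about right, observed percentages 2 to 3 points too high.
- Imputation from the continuous scores: 62.3% v 70.4%, odds ratio 1.44. The simulated data suit the imputation model, so this is a favourable test.

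**6. Against sampling error.** With 530 per arm and the true rates of simulation B, the unadjusted variance of the log odds ratio is 1/(530 × 0.624 × 0.376) + 1/(530 × 0.703 × 0.297) = 0.0171, so the standard error is 0.13. The shifts are ln(1.43/1.37) = 0.043 and ln(1.43/1.35) = 0.058, or 0.33 and 0.44 standard errors.

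**7. ASD.** An unstructured matrix for 52 weeks has 52 × 51/2 = 1,326 correlations. SAP 4.2.5.1 gives a fallback sequence for the MMRM; 4.2.5.4 gives none. Falling back to independence would lose the protection shown in step 3.

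**The case against.** The strongest reply is that the planned GEE is better protected than it looks. Missingness that depends only on treatment, visit, region, age group or baseline score does no harm, because all are in the model. The unstructured working correlation then removes most of what remains. A reader might infer that the analysis is valid only if data are missing completely at random; that is too strong for this model. Nor does it discard subjects: a missing visit drops out, but the subject's other visits stay.

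Missing data should also be limited. Subjects who stop treatment are followed to Week 52, and under Option 2 they keep the diary and may complete the clinic questionnaires at home (Protocol 7.1.1). SAP 4.2.5.1 attributes missing questionnaire data mainly to loss to follow-up, death, withdrawal of consent and Option 3. The protocol delegated both model details and missing-data handling to the SAP, so the gap in Section 6 is one of documentation.

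All of this stands. It does not supply a stated assumption or a sensitivity analysis for the responder endpoints. Option 3 missingness follows a decision taken after randomisation, so baseline covariates need not explain it.

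A reader might also take the DRMI analyses as a sign that the sponsor expects dropout to depend on treatment. SAP 4.2.4.2 presents controlled imputation as a test of departures from the assumptions, not a forecast. DRMI is also a missing-not-at-random analysis, which a MAR-based responder analysis would not replace.

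**Conclusion.** The point holds in limited form, as something to consider. The responder GEE rests on a missing-data assumption that is unstated and differs from that of the continuous analyses, and nothing in the plan tests it.

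The odds ratio is modestly biased when score-dependent dropout differs between arms: less than half a standard error in simulation B. In simulation A, heavier placebo dropout pulled it towards 1 and heavier tezepelumab dropout pushed it away, so the documents support no claim about direction. With similar dropout in both arms, the main distortion is in observed-case percentages: 2 to 3 points at about 10% dropout and about 5 points at 20%. The 4.6 v 7.9 point contrast describes raw percentages with an observed-case denominator, which the SAP does not confirm; it is not the GEE result.

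These sizes rest on assumed correlations, dropout models and response rates. Only AQLQ(S)+12 was simulated; ACQ-6 and ASD have more time points.

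It would be wrong to infer that the key secondary conclusions are at risk. The responder analyses are supportive and outside the testing hierarchy, and the continuous endpoints have their own MAR, DRMI and tipping-point analyses.

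**What to change.** In SAP 4.2.5.4:

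- Add a Week 52 responder analysis for each scale, with responder status derived from the 100 MAR-imputed datasets planned in 4.2.5.2. Those datasets impute absolute scores and then compute change from baseline, so the 0.5 threshold can be applied directly. State whether imputed scores are first rounded to the scale's steps.
- In each dataset, fit the protocol's logistic regression (treatment, region, age group, baseline score) and combine with Rubin's rules.
- Report responder percentages from those datasets beside the observed ones, with the denominator stated.
- Keep the GEE, state its missing-data assumption, and name a fallback working correlation for ASD.

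In SAP Section 6, list the change from logistic regression to GEE.

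The cost is SAP wording and one extra run on datasets that will already exist. The added estimate depends on the imputation model, but the plan already relies on that model for the same scores. It addresses MAR only; responder versions of the DRMI datasets could be derived in the same way if wanted.

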9.4.3.3 Analysis of other efficacy endpoints

Annual rates for other relevant endpoints will be summarized descriptively and analyzed using a similar model as for the primary endpoint (Section 9.4.3.1).

Other binary endpoints will be summarized descriptively and analyzed using a logistic regression model with factors which will include treatment, region and age (adolescents or adults). Baseline

of the corresponding endpoint will also be included in the model (where relevant) as a continuous linear covariate.

Other continuous endpoints will be summarized descriptively and analyzed using an MMRM model analogous to that specified for key secondary endpoints (Section 9.4.3.2). Log transformation of endpoints prior to implementing the MMRM will be considered for continuous endpoints which do not meet the distributional assumptions, and this will be pre-specified in the SAP where possible.

Time to first asthma exacerbation will be summarized graphically using Kaplan-Meier estimates, and analyzed using a Cox proportional hazards model with factors for treatment, region, age (adolescents or adults), and history of exacerbations (2 or >2 in previous 12 months).

Further details of statistical models for other efficacy endpoints will be specified in the SAP, including details of how missing data and data collected after premature discontinuation of study medication will be handled.

Sensitivity and subgroup analyses will not be performed on other efficacy endpoints, unless specified otherwise in the SAP.

9.4.4 Safety analyses

Adverse events will be coded using the Medical Dictionary for Regulatory Activities (MedDRA) version in force at each database lock. The definition of on-treatment and on-study for adverse event analyses will be given in the SAP.

The number and percentage of subjects with on-treatment and on-study adverse events will be tabulated separately by preferred term and system organ class. An event that occurred one or more times during a period will contribute 1 observation to the numerator of the proportion. The denominator of the proportion will comprise all subjects in the safety population. On-treatment adverse events will also be summarized by intensity/severity and separately, by causality/relatedness (as determined by the investigator). Should a subject report the same preferred term/system organ class within multiple intensity/severity or causality/relatedness categories, the subject's worst occurrence (most severe/most related) will be tabulated. Serious AEs, AEs leading to discontinuation from IP, and commonly occurring AEs will be summarized in a generally similar manner. Adverse events, SAEs, AEs leading to death, and AEs leading to discontinuation of IP will be summarized for each treatment group as applicable.

An overall summary of on-treatment AEs will be presented by treatment group adjusted for subject exposure to treatment.

AEs of Special Interest (AESIs), as defined in [Section 8.3.8](#) will also be summarized descriptively by treatment group.

Laboratory data will be summarized by presenting shift tables using normal ranges (baseline to most extreme post-baseline value) and by presenting summary statistics of observed and change from baseline values (means, medians, quartiles, ranges). The incidence of clinically notable laboratory abnormalities will be summarized.

Vital signs data will be summarized by presenting summary statistics of observed and change from baseline values. The incidence of clinically notable vital signs abnormalities will be summarized. Abnormal ECGs as per Investigator's overall interpretation will be summarized.

9.4.5 Other analyses

PK, pharmacodynamic, and biomarker exploratory analyses will be described in the statistical analysis plan finalized before primary database lock. The population PK analysis and pharmacodynamic analyses will be presented separately from the main clinical study report (CSR).

The prevalence and incidence of anti-drug antibodies (ADA) will be reported by treatment group. ADA data will be summarized using descriptive statistics at each visit by treatment group. Samples confirmed positive for ADA will be tested for neutralizing antibodies (nAb), and the nAb status will be summarized by treatment group. The potential effects of ADA status and ADA titer on pharmacokinetics of tezepelumab will be evaluated. The potential association of ADA status, ADA titer, and nAb status with efficacy will be evaluated. The potential association of ADA status with safety may be evaluated.

Additional analyses assessing the impact of COVID-19 may be included in the SAP.

